8.2.5. Laboratory Tests

[Appendix 2](#) lists the clinical laboratory tests to be performed, and the SoA specifies when samples are routinely collected for clinical laboratory tests. Samples for laboratory testing will be obtained in the event of anaphylaxis or generalized urticaria, as described in Section 8.3.6.1 and

[Appendix 2](#), Section 10.2.2. Additional tests may be performed at any time during the study, as determined necessary by the investigator or as required by local regulations.

All protocol-required laboratory assessments, as defined in [Appendix 2](#), must be conducted in accordance with the SoA, standard collection requirements, and laboratory manual.

If laboratory values from nonprotocol specified laboratory assessments performed at an investigator-designated local laboratory require a change in participant management or are considered clinically significant by the investigator (for example, SAE, AE, or dose modification), then report the information as an AE.

Reviewing and recording test results

The investigator must review the laboratory results, document this review, and report any clinically relevant changes occurring during the study as an AE. The laboratory results must be retained with source documents, unless a Source Document Agreement or comparable document cites an electronic location that accommodates the expected retention duration.

Repeat testing after clinically significant abnormal findings

All laboratory tests with values considered clinically significantly abnormal during participation in the study or within 8 weeks after the last dose of study intervention should be repeated until the values return to normal or baseline or are no longer considered clinically significant by the investigator or the medical monitor. If such values do not return to normal/baseline within a period of time judged reasonable by the investigator, the etiology should be identified and the sponsor notified.

Blinding of laboratory test results

Laboratory results that could unblind the study will not be reported to investigative sites or other blinded personnel.

Sample retention

Unless otherwise specified in the subsections of Section 8 or in [Appendix 1](#), Section 10.1.12, all samples collected for specified laboratory tests will be destroyed within 60 days of receipt of confirmed test results. Certain samples may be retained for a longer period, if necessary, to comply with applicable laws, regulations, or laboratory certification standards.

8.2.5.1. Pregnancy Testing

Pregnancy testing is to be performed on WOCBP and women with a history of tubal ligation. Participants who are pregnant will be discontinued from the study (Section 7).

Pregnancy testing visits and times

Serum pregnancy test will be done at screening only, and results will be confirmed by the central laboratory.

Urine pregnancy testing will be performed locally when specified in the SoA. If the specified visit includes study drug administration, the urine pregnancy test must be “negative” within 24 hours before the study drug is administered.

Urine pregnancy testing may be performed at additional time points during the study treatment period and/or follow-up period, at the discretion of the investigator or if this is required by local regulations.

If a urine pregnancy test is not available, a local serum pregnancy test is an acceptable alternative.

Optional FSH testing

The participant's FSH level can be obtained during screening at the discretion of the investigator to assist in determining whether a woman meets the definition of "postmenopausal." The FSH level can also be optionally obtained during the study to determine the participant's postmenopausal status (see the SoA and [Appendix 4](#)).

8.2.6. Tuberculosis Testing and Monitoring

Tuberculosis testing

During screening, all participants are to be assessed for risk factors, symptoms, and signs of TB with all of the following:

- Thorough history to determine the lifetime risk factors for
 - TB infection
 - TB progression, and
 - symptoms and/or signs of active TB, and
- Signs of previous or active TB by means of
 - thorough physical examination for signs of active TB, including
 - measurement of body temperature (Section [8.2.1](#)), and
 - assessment of peripheral lymph nodes (Section [8.2.2](#)), and
 - posterior-anterior CXR interpreted and reported by radiologist or pulmonologist (Section [8.2.4](#)).

All participants with no history of LTBI or active TB, and no history of positive Mantoux TST using PPD or positive *Mycobacterium tuberculosis* IGRA must have 1 of the following:

- PPD TST
 - The TST is performed by injecting 0.1 mL of tuberculin PPD into the inner surface of the forearm. The injection should be made with a tuberculin syringe, with the needle bevel facing upward. The TST is an intradermal injection. When placed correctly, the injection should produce a pale elevation of the skin (a wheal) 6 to 10 mm in diameter. Measure induration at site of intradermal

injection 48 to 72 hours after intradermal injection. The test must be read during this window of time. The reaction should be measured in millimeters of induration (palpable, raised, hardened area, or swelling). The reader should not measure erythema (redness). The diameter of the indurated area should be measured across the forearm (perpendicular to the long axis).

- An induration of 5 or more millimeters is considered positive.
- Two-step testing (repeat TST from 1 to 3 weeks after the first TST) is recommended for certain participant groups, based on investigator judgment, including
 - persons receiving immunosuppressant treatment
 - persons with a history of temporally remote increased risk of TB infection, and
 - persons for whom the first test is negative, as per local public health and/or professional medical society recommendations.
- IGRA for *Mycobacterium tuberculosis*. Ensure that specimen handling, transport, timing, and laboratory procedures meet all requirements per package insert.

Retesting

One retest is allowed for participants with an “indeterminate” QuantiFERON-TB Gold assay or “borderline” T-SPOT.TB assay. Participants with 2 indeterminate QuantiFERON-TB Gold assays or 2 borderline T-SPOT.TB assays will be excluded.

Diagnosed LTBI

Participants diagnosed with LTBI, or have had LTBI that has not been treated with a complete course of appropriate therapy as defined by the WHO and/or the United States Centers for Disease Control and Prevention, are excluded (Section 5.2).

Monitoring during the study

For all participants, monitoring for TB is to be continuous throughout the study. At a minimum, each participant is to have the following documented at least approximately every 3 to 4 months:

- thorough history to determine any risk factors for TB infection and for TB progression, symptoms or signs of active TB, and
- physical examination that includes assessment for signs of active TB, including measurement of body temperature and assessment of peripheral lymph nodes (Section 8.2.2).

8.2.7. Hepatitis B Testing and Monitoring

Initial testing for HBV infection includes hepatitis B surface antigen (HBsAg) and antibody to hepatitis B core antigen (anti-HBc).

- If HBsAg is positive, the participant is excluded.
- If HBsAg is negative and anti-HBc is negative, the participant is not excluded.
- If HBsAg is negative and anti-HBc is positive, further testing for HBV DNA is required.
 - If the screening HBV DNA is positive, the participant is excluded.
 - If the screening HBV DNA is negative, the participant is not excluded. Repeat testing for HBV DNA is required at least approximately every 8 to 14 weeks during the study (see the timing in the SoA), with temporary withholding or permanent discontinuation of study intervention if HBV DNA is positive, as described in Section 7.

Management of enrolled participants with detectable HBV DNA during the study

If HBV DNA is detected during the study, the study drug will be temporarily withheld or discontinued and participants should receive appropriate follow-up medical care as described in Section 7.

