For procedures at an unscheduled visit, see V997 in Table 4.											
Visits 10 through 28 are eligible to be conducted remotely (that is, by telephone, IT-assisted virtual visit, mobile healthcare, or a combination thereof) if written approval is provided by the sponsor and according to the preferences of the participant and the study site. However, no more than 34 days can elapse without an on-site study visit occurring.											
Visit number	V20	V21	V22	V23	V24	V25	V26	V27	V28	V29	Comment
Weeks from randomization	34	36	38	40	42	44	46	48	50	52	
Study day	239	253	267	281	295	309	323	337	351	365	
Visit interval tolerance (days)	±3	±3	±3	±3	±3	±3	±3	±3	±3	±3	
Fasting visit										X	
Laboratory Tests and Sample Collections											
Hematology		X		X		X		X		X	
Clinical chemistry		X		X		X		X		X	
Lipid panel										X	Fasting samples are preferred, but if participant is nonfasting at time of collection, this is not a protocol deviation.
Urinalysis										X	
Urine pregnancy (local)		X		X		X		X		X	Perform only for women of childbearing potential and women with a history of tubal ligation. At dosing visits which have pregnancy testing, the pregnancy test result must be confirmed to be negative prior to dosing. Pregnancy testing may be performed more frequently than designated on the SoA, if local laws or regulations require more frequent testing.
CCI										X	
HBV DNA		X						X			Only for participants who are positive for anti-HBc at screening.

Table 2 (continued). Schedule of activities for the Maintenance Treatment Period of Study J1P-MC-KFAH											
This schedule applies to study participants who are responders at Week 12.											
For procedures at an early termination visit, see ETV in Table 4.											
For procedures at an unscheduled visit, see V997 in Table 4.											
Visits 10 through 28 are eligible to be conducted remotely (that is, by telephone, IT-assisted virtual visit, mobile healthcare, or a combination thereof) if written approval is provided by the sponsor and according to the preferences of the participant and the study site. However, no more than 34 days can elapse without an on-site study visit occurring.											
Visit number	V20	V21	V22	V23	V24	V25	V26	V27	V28	V29	Comment
Weeks from randomization	34	36	38	40	42	44	46	48	50	52	
Study day	239	253	267	281	295	309	323	337	351	365	
Visit interval tolerance (days)	±3	±3	±3	±3	±3	±3	±3	±3	±3	±3	
Fasting visit										X	

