1.3.4. Schedule of activities for ETV, unscheduled visits, and Post-Treatment Follow-Up Period

Table 4. Schedule of Activities for Early Termination, Unscheduled Visits, and Post-Treatment Follow-Up Period					
V802 is only for randomized participants who were positive for anti-HBc at screening. All other participants will have their final visit at V801 or ETV.					
V997: Additional study procedures can be performed at the discretion of the investigator.					
Visit number	ETV	V997	V801	V802	Comment
Weeks from randomization	—	—	58 or ETV + 8 weeks after last dose	66 or ETV + 16 weeks after last dose	The intervals between ETV and the post-treatment follow-up visit(s) should be adequate to ensure that V801 occurs at least 8 weeks since last dose and V802 (if applicable) occurs at least 16 weeks since last dose.
Study day	—	—	—	—	
Visit interval tolerance (days)	—	—	±7	±7	
Fasting visit					No fasting in this period
Concomitant medications	X	X	X	X	
Adverse events	X	X	X	X	For AESIs, additional data are collected (Section 8.3.6).
Review modified Mayo score (MMS)	X				
Tobacco use	X				
Physical Evaluation					
Weight	X		X		
Vital signs	X	X	X	X	Blood pressure, body temperature, and pulse rate. Vital signs should be measured after participant has been sitting for at least 5 minutes. V997: Vital signs collection is optional.
Symptom-directed physical examination, including assessment for signs and symptoms of tuberculosis (TB), including peripheral lymph nodes	X		X	X	See Section 8.2.2.
CCI	X		X	X	
12-lead electrocardiogram (ECG)	X				Locally performed.
Patient Diary (Electronic)					
Diary return	X				
Patient-Reported Outcomes (Electronic)					
Inflammatory Bowel Disease Questionnaire (IBDQ)	X				
Patient Global Impression of Change (PGI-C)	X				

Table 4. Schedule of Activities for Early Termination, Unscheduled Visits, and Post-Treatment Follow-Up Period					
V802 is only for randomized participants who were positive for anti-HBc at screening. All other participants will have their final visit at V801 or ETV.					
V997: Additional study procedures can be performed at the discretion of the investigator.					
Visit number	ETV	V997	V801	V802	Comment
Weeks from randomization	—	—	58 or ETV + 8 weeks after last dose	66 or ETV + 16 weeks after last dose	The intervals between ETV and the post-treatment follow-up visit(s) should be adequate to ensure that V801 occurs at least 8 weeks since last dose and V802 (if applicable) occurs at least 16 weeks since last dose.

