Study day	—	—	—	—	
Visit interval tolerance (days)	—	—	±7	±7	
Fasting visit					No fasting in this period
QIDS-SR16	X				
Clinician-Administered Questionnaires (Paper)					
Physician’s Global Assessment (PGA)	X				
Laboratory Tests and Sample Collections					
Hematology	X		X	X	
Clinical chemistry	X		X	X	
Lipid panel	X				Fasting is not required for the lipid panel at ETV.
Urinalysis	X		X	X	
Urine pregnancy (local)	X		X	X	Perform only for women of childbearing potential and women with a history of tubal ligation. At dosing visits which have pregnancy testing, the pregnancy test result must be confirmed to be negative prior to dosing. Pregnancy testing may be performed more frequently than designated on the SoA if local laws or regulations require more frequent testing.
CCI	X				
HBV DNA	X			X	Only for participants who are positive for anti-HBc at screening.
Pharmacokinetic (PK) samples	X		X		Collect samples before dosing, if dosing is scheduled. Collect additional samples at specified times relative to onset of hypersensitivity events.

Table 4. Schedule of Activities for Early Termination, Unscheduled Visits, and Post-Treatment Follow-Up Period					
V802 is only for randomized participants who were positive for anti-HBc at screening. All other participants will have their final visit at V801 or ETV.					
V997: Additional study procedures can be performed at the discretion of the investigator.					
Visit number	ETV	V997	V801	V802	Comment
Weeks from randomization	—	—	58 or ETV + 8 weeks after last dose	66 or ETV + 16 weeks after last dose	The intervals between ETV and the post-treatment follow-up visit(s) should be adequate to ensure that V801 occurs at least 8 weeks since last dose and V802 (if applicable) occurs at least 16 weeks since last dose.
Study day	—	—	—	—	
Visit interval tolerance (days)	—	—	±7	±7	
Fasting visit					No fasting in this period
CCI	X		X		Collect samples before dosing, if dosing is scheduled. Collect additional samples at specified times relative to onset of hypersensitivity events.
Flow cytometry panel	X				
Genetics sample					Blood sample for DNA pharmacogenetics can be obtained any time at or after V2.
CCI	X				
Endoscopic Procedure					
Endoscopy	X				Recommended at ETV based on judgment of the investigator and after discussion with the sponsor’s medical monitor. If not performed at ETV, this will not be considered a protocol deviation.

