The sponsor intends for the transition from Stage 1 to Stage 2 to be seamless, with participant screening and enrollment activities occurring continuously in the transition period. The study IWRS will allocate newly enrolling participants to groups according to the Stage 1 randomization ratio until the Stage 2 groups have been decided upon and implemented. The randomization ratios are described in Section 9.2.

Study Periods

This study has multiple periods, as shown the schema in Section 1.2.

Screening period

This period begins with Visit 1, which occurs 5 weeks (or less) before the planned randomization visit. A participant's screening evaluations must be completed and reviewed to confirm the participant's eligibility before randomization and dosing occurs at Visit 2.

Blinded induction and blinded maintenance periods

The double-blind, placebo-controlled, 12-week induction treatment period begins at Visit 2. Dosing, sample collection, and assessments continue Q2W, as shown in the SOA. Between Week 12 and Week 14, based on samples and assessments collected at Week 12, participants will be classified as either "Week 12 Responders" or "Week 12 Nonresponders" based on the "clinical response" criteria defined in Section 8.1.

- "Week 12 Responders" will continue to receive their same randomly assigned treatment throughout the blinded 40-week Maintenance Period, with the final dose occurring at Week 50 and the last maintenance assessments and sample collections at Week 52.
- "Week 12 Nonresponders" will enter the Extension Induction and Extension Maintenance Periods.

Extension induction and maintenance periods

Beginning at Week 14, participants who were classified as Week 12 Nonresponders will receive the high dose (CC1 μ g) of LY3471851 Q2W, unless a lower dose is selected for Stage 2 based on interim analyses.

Between Week 26 and Week 28, based on samples and assessments collected at Week 26, these participants will again be classified according to their response status (responder or nonresponder).

- Participants who are classified as responders based on the samples and assessments at Week 26 will continue to receive LY3471851 Q2W as maintenance through the remainder of the study. These participants have their final dose at Week 50 and their last maintenance assessments and sample collections at Week 52.

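### Participants positive for anti-HBc who complete treatment go 18 weeks (Week 48 to Week 66) without a scheduled HBV DNA test, although the protocol sets an upper limit of about 14 weeks; a test at V801 would close the gap

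*Protocol*

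**What the plan says.** Protocol Section 8.2.7 admits participants who are HBsAg negative, anti-HBc positive and HBV DNA negative, on condition of monitoring: "Repeat testing for HBV DNA is required at least approximately every 8 to 14 weeks during the study". The sentence points to the Schedule of Activities for timing and then gives the consequence of a positive result: "with temporary withholding or permanent discontinuation of study intervention if HBV DNA is positive, as described in Section 7". The management paragraph adds a second duty when HBV DNA is detected: "participants should receive appropriate follow-up medical care as described in Section 7".

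The HBV DNA rows of the schedule carry the comment "Only for participants who are positive for anti-HBc at screening" and are marked as follows:

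- Table 1 (screening and induction): V1 and V9 (Week 12).
- Table 2 (maintenance, Week 12 responders): V15, V21 and V27 (Weeks 24, 36 and 48). Blank at V29 (Week 52).
- Table 3 (extension, Week 12 nonresponders): V16, V22 and V27 (Weeks 26, 38 and 48). Blank at V29.
- Table 4 (early termination and follow-up): ETV and V802. Blank at V801 (Week 58).

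Table 4 times V802 at "66 or ETV + 16 weeks after last dose" and restricts it: "V802 is only for randomized participants who were positive for anti-HBc at screening". Section 4.1 places the last dose at Week 50.

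**The concern.** Section 8.2.7 leaves its execution to the schedule, and after Week 48 the schedule does not deliver the stated interval. The follow-up period counts as part of the study: Section 4.4 defines completion by the last visit in the schedule, and the Synopsis includes post-treatment follow-up in the study duration. V802 exists only for this subset and includes HBV DNA, so the sponsor evidently meant surveillance for hepatitis B to continue after dosing.

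The interval is not wholly off drug either. Doses are given at Week 48, after that visit's sample, and at Week 50, and Section 4.2 puts the mean half-life at 8 to 13 days. No scheduled HBV DNA test covers the last two doses or the washout until V802.

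At stake is how early reactivation is found in people admitted on condition of monitoring. The stop-dosing action has lapsed by then, but the duty to arrange follow-up care has not.

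**Working it through.** **Inputs.** Visit weeks and windows come from schedule Tables 1 to 4: V27 Week 48 ±3 days, V801 Week 58 ±7 days, V802 Week 66 ±7 days. Study day = 7 × week + 1, which gives V27 = 337, V801 = 407 and V802 = 463. The limit is 14 weeks = 98 days.

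**Nominal intervals between tests from Week 12 on.**

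| Pathway | Test weeks | Intervals (weeks) |
|---|---|---|
| Maintenance | 12, 24, 36, 48, 66 | 12, 12, 12, **18** |
| Extension | 12, 26, 38, 48, 66 | 14, 12, 10, **18** |

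The schedule fits the 8-to-14-week rule from Week 12 to Week 48 and breaks it in the last interval on both pathways.

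**V27 to V802 with windows.** 463 − 337 = 126 days. The windows add or subtract 3 + 7 = 10 days, so the range is 116 to 136 days (16.6 to 19.4 weeks). The excess over 98 days is 18 to 38 days.

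Table 4 also comments on spacing: "V801 occurs at least 8 weeks since last dose and V802 (if applicable) occurs at least 16 weeks since last dose". If that minimum is applied to completers, the earliest Week 50 dose is day 351 − 3 = 348, V802 cannot precede day 348 + 112 = 460, and the shortest interval from the latest V27 (day 340) is 460 − 340 = 120 days. The shortest case then exceeds the limit by 22 days instead of 18.

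**With a test at V801.**

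- V27 to V801: 407 − 337 = 70 ± 10 = 60 to 80 days (8.6 to 11.4 weeks).
- V801 to V802: 463 − 407 = 56 ± 14 = 42 to 70 days (6.0 to 10.0 weeks).

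Both are below 98 days at every permitted timing. Applying the minimum spacing after the last dose would raise the lower ends slightly and leave that result unchanged.

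**Early terminators.** The documents do not fix the time from last dose to ETV. Assuming 0 to 14 days, ETV to V802 is nominally 112 − 0 = 112 days down to 112 − 14 = 98 days (16 to 14 weeks). A V801 test would split this into 56 to 42 days, then 56 days.

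**Screening to V9 (a separate interval).** Section 4.1 says of screening: "This period begins with Visit 1, which occurs 5 weeks (or less) before the planned randomization visit". The longest interval is 35 + 84 + 3 = 122 days (17.4 weeks), 24 days over. It stays within 98 days if the screening sample is drawn no more than 98 − 84 = 14 days before V2, or 98 − 87 = 11 days if V9 is 3 days late. This depends on when the sample is drawn, whereas the Week 48 to Week 66 interval is out of range for every completer.

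**The case against.** The rule is worded as approximate and defers to the schedule, and the schedule tells sites exactly when to sample. Its stated action is about dosing. Week 48 is the second-to-last dosing visit, the on-treatment intervals conform, and V802 can be read as a deliberate single off-drug check. Chemistry at Weeks 52, 58 and 66 leads into the work-up in Section 8.2.9, and Section 8.2.5 lets the investigator order extra tests at any time. The documents give no off-drug reactivation risk for this drug, and no efficacy analysis depends on these samples. Rewording Section 8.2.7 to cover only the treatment period plus V802 would remove the mismatch without another assay.

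Much of this stands as a limit on importance. It does not remove the point:

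- The word *approximately* can absorb a visit window, such as the 92 to 104 days possible between V9 and V16. It does not cover a planned 18 weeks.
- An on-treatment reading is not what the text says, and it sits poorly with a follow-up visit created for this subset.
- The liver work-up starts only when thresholds are crossed. For transaminases, repeat testing begins at 3 times ULN, and viral hepatitis tests are called for at 5 times ULN, or at 3 times with signs or symptoms. Appendix 5 makes HBV DNA in that panel dependent on regulatory requirements or test availability.
- Investigator-ordered testing is discretionary.
- Rewording would make the documents agree but leave detection as late as it is now.

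**Conclusion.** The concern holds. As written, the schedule misses the protocol's own required interval for every anti-HBc-positive completer: 18 weeks nominally and 116 to 136 days with windows (at least 120 if the 16-week minimum after the last dose binds), against 98. This rests only on the schedule tables and on follow-up counting as part of the study, which Section 4.4 supports.

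The consequence is modest. A V801 result could not alter dosing, and enzyme elevations would be picked up through chemistry. What remains is viremia below the Section 8.2.9 thresholds, found on schedule up to about 8 weeks later than with a V801 test, with the follow-up care delayed accordingly. The number of affected participants cannot be stated, because the documents do not give the size of the anti-HBc-positive subset. The early-terminator figures depend on the assumed 0 to 14 days from last dose to ETV. It should be corrected because it is a stated safety requirement and the correction is cheap.

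**What to change.** In Table 4, mark HBV DNA at V801 for participants who were anti-HBc positive at screening. Completer intervals become 10 and 8 weeks. V801 is the better place than V29 because it also shortens the ETV-to-V802 interval for early terminators, who under Section 6.5 and Appendix 7 may start otherwise prohibited immunosuppressive drugs once the ETV is done.

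The cost is one table entry in an amendment and one assay per anti-HBc-positive participant. V801 already includes hematology and chemistry, so no new visit or separate blood draw is needed.

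Optionally, and as a separate matter, an HBV DNA sample at V2 would make the first on-treatment interval 84 ± 3 = 81 to 87 days, whatever the date of the screening sample. The V801 test does not address that interval.
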